## 1.0 Objectives / Specific Aims

Posttraumatic stress disorder (PTSD) is a debilitating mental health condition that increases suicide risk and affects up to 20% of military veterans and 8% of the general population. Prolonged Exposure (PE) is a highly efficacious, evidence-based, cognitive-behavioral therapy for PTSD. However, dropout rates are high (25-30%) and an estimated one-third of patients who complete PE remain symptomatic. The primary objective of this study is to test a technology-based system that will (1) enable clinicians and clinical support staff to virtually accompany patients during in vivo exposures (IVEs) exercises to enhance engagement and successful completion of the exercises, and (2) provide clinicians and clinical support staff with real-time streaming of physiological biomarkers of affective engagement--galvanic skin response (GSR) and heart rate (HR)--and subjective units of distress (SUDS). This *actionable data* will be used in real-time by clinicians to modify the exercises and avoid under- and over-engagement, thereby minimizing inefficiencies and maximizing therapeutic value of IVEs. Secondary objectives are to use *passive data* collection to characterize IVEs, identify predictors of change, and inform next steps. To accomplish this, Zeriscope, a local small business with experience developing cutting-edge mobile technology platforms for health care, has partnered with clinical researchers at the Medical University of South Carolina (MUSC) to (1) develop a technology-based system to use intelligent biometrics (IB) to optimize PE ("IB-PE"), and (2) compare the guided IVE intervention to a passive data record-only version which will collect and store biometric and behavioral data for offline analyses. The following Specific Aim is proposed:

**Specific Aim:** **Conduct a 10-session randomized clinical trial (N=40 treatment-seeking veterans/civilians with current PTSD) to evaluate the acceptability and preliminary efficacy of IB-PE and investigate predictors of outcome.** Milestones: (1a) Evaluate ability of IB-PE (guided vs. record only) in reducing PTSD severity from baseline to session 10; and (2b) Use GSR, HR and SUDS to characterize IVEs and identify how each of these indicators predicts treatment response.

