VA/Department of Defense Clinical Practice Guidelines (The Management of Posttraumatic Stress Disorder Work Group, 2017) and other professional organizations, (Forbes et al., 2010; Agency for Healthcare Research and Quality, 2014) and is widely disseminated throughout the VA healthcare system. Key components of PE are *imaginal exposure* (revisiting the trauma memory during therapy sessions) and *in vivo exposure (IVE)* (approaching avoided but objectively safe stimuli in the “real world” such as crowded stores that serve as reminders of the trauma). Both imaginal and in vivo exposures are designed to activate pathological fear structures and provide corrective information in order to alter maladaptive behaviors and thoughts (Foa & Kozak, 1986; Foa & McLean, 2016). *Physiological indicators of distress (e.g., heart rate, skin conductance) are objective indices of activation and extinction learning, and numerous studies show that greater activation and reactivity before and during PE therapy is associated with improved treatment outcomes* (Foa, 1997; Jaycox, Foa, & Morral, 1998; Norrholm et al., 2016; Rauch et al., 2015; Rothbaum et al., 2014; Wangelin & Tuerk, 2015). The new system to be developed in the proposed study will monitor physiological activation so that if a patient is under-engaged, adjustments can be made in real-time to increase activation and enhance extinction learning.

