IVE is crucial to exposure therapy in order to ensure the new knowledge and behaviors learned in the office are successfully transferred to patients’ “real world” environments. Although IVE is a fundamental component of exposure therapy for PTSD (and anxiety disorders), surprisingly little research has addressed this critical aspect of treatment. Substantial gaps exist in our understanding of what occurs during IVE, and which psychophysiological, behavioral, or contextual factors are predictive of treatment response. This critical gap of knowledge is due, in large part, to the fact that IVEs are conducted outside the office and are “invisible” to the provider. In rare cases, therapists leave the office and literally go to exposure sites with patients, an inefficient and unsustainable practice. More commonly, patients are given in vivo assignments to complete in-between therapy sessions (e.g., visit Walmart twice next week during lunchtime) and report back to the therapist at the next session (Foa, Hembree, & Rothbaum, 2007). This approach has numerous shortcomings; some patients fail to attempt the exercises (e.g., given high avoidance symptoms) and other patients attempt the exercises but are under- or over-engaged, both of which confer suboptimal treatment response. At present, providers are reliant upon patient self-report, which is subject to inaccuracies due to retrospective memory or survey bias (National Advisory Mental Health Council, 2019). This study leverages recent advances in mobile technology to mitigate these shortcomings by enabling the clinical team to virtually monitor and modify, in real-time, IVEs based on patient-specific physiological and subjective data to optimize treatment engagement and maximize the therapeutic value of IVEs.

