
**Figure 3. Overview of the randomized clinical trial.** Participants (N=40) randomized to 10 sessions of PE (once or twice weekly visits) and either a) PE with guided IVEs using Intelligent Biometrics (IB-PE Guided) or b) PE alone (IB-PE Non-guided).

How the IVE Coach will guide the patient through IVEs: While there will be some variability based on individual patients and specific in vivo activities, the patient and IVE Coach will use synchronous audio/video to communicate, and will provide a brief (3 min) review of the instructions before the patient begins the IVE. In addition, a baseline for each IVE will be established prior to beginning the IVE exercise. If the patient is optimally engaged in the exercise, as demonstrated by increasing physiological (e.g. skin conductance, heart rate) and subjective (increase in SUDS scores) indices, the IVE Coach will provide

encouragement to continue but will not interrupt the patient. If the patient is not engaged (e.g., showing low/no increase in physiological and subjective indices of engagement, not following instructions, engaging in distraction behaviors), the IVE Coach will intervene and review the instructions, provide specific guidance to help the patient engage, and provide feedback until the patient is optimally engaged to maximize benefits. After the IVE, a brief (5 min) processing will occur. The IVE Coach will ask the patient how he/she thinks the exercise went, what was learned, and plan the next IVE. The IVE Coach will complete a check-out form documenting how the exercise went and will communicate this with the clinical support team.

**Telehealth:** Participants in this research study may choose to complete informed consent/baseline appointment, study visits and therapy sessions via home-based telehealth (HBT) care (i.e., service delivery to patients in their homes using consumer-friendly, video-conferencing technology) which may likely enhance retention by directly circumventing financial and transportation barriers associated with traveling to MUSC/VA for in-person sessions. HBT sessions will be delivered via standard desk, laptop computer, tablet, or smartphone running MUSC/VA approved applications.

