**General Statistical Analyses.** All analyses will be performed on the intent-to-treat sample consisting of all randomized subjects. Baseline clinical and demographic characteristics will be collected and t-tests, chi-square tests, or their non-parametric equivalents will test for group differences, as appropriate, in SAS v9.4 (SAS Institute, Cary, NC, USA). Baseline characteristics that are associated with the primary outcome measures will be included as covariates in subsequent analyses. For all analyses, alpha will be set at 0.05. Urn randomization will be stratified by PTSD severity (CAP-5 total score at baseline). Based on our sample size and assuming 20% attrition (N=32), we have 80% power to detect a large effect (Cohen's  $d = 1.02$ ) for treatment outcome at a probability level of 0.05 for a two-tailed test (Cohen, 1988).

Hypothesis 1: IB-PE will be feasible and acceptable, as evidenced by at least 80% of participants (a) being able to turn on/off the equipment in  $\leq 5$  minutes; (b) reporting positive perceptions toward IB-PE via self-report assessments (Sekhon, Cartwright, & Francis, 2017). Hypothesis 2: Participants in the IB-PE guided group will evidence significantly greater pre- to post-treatment reductions in PTSD severity as compared to the record-only group. To test this hypothesis, independent generalized linear mixed effects models will be used to examine PCL-5 and CAPS-5 scores at final session by group. Models will be adjusted, respectively, for baseline PCL-5 and CAPS-5. Group will be entered as the predictor variable. Hypothesis 3: Higher levels of physiological and subjective engagement will predict greater treatment response. To test this hypothesis, mean HR, GSR, and SUDS responses during IVEs will be calculated according to previously published methods (Norholm et al., 2016; Rauch et al., 2018; Rothbaum et al., 2014) and multilevel modeling (MLM) will be used to analyze these variables as predictors of CAPS-5 at final session within and between treatment groups.

Exploratory analyses will examine group differences in the number of sessions required to attain significant symptom improvement on the PCL-5 from baseline (Rothbaum et al., 2014) and durability of effects at 1-month follow up. Data from both groups will be harnessed to explore the development of patient-specific algorithms predicting optimal engagement during IVE.

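### Hypothesis 3 expects more engagement to be better, while the protocol also says over-engagement harms response, and no curved term is named to tell the two apart

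*Combined protocol and SAP*

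**What the plan says.** The protocol makes two kinds of statement about engagement during in vivo exposures.

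**An optimum.** Section 1.0 says clinicians will use the real-time data to "modify the exercises and avoid under- and over-engagement". Section 2.0, on in vivo exposure, says that "other patients attempt the exercises but are under- or over-engaged, both of which confer suboptimal treatment response".

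**One direction.** Section 2.0, on Prolonged Exposure, reports that "greater activation and reactivity before and during PE therapy is associated with improved treatment outcomes" and describes only an upward correction: "if a patient is under-engaged, adjustments can be made in real-time to increase activation". Hypothesis 3 in section 11.0 follows this line: "Higher levels of physiological and subjective engagement will predict greater treatment response". Mean HR, GSR and SUDS during exposures are to be analysed by multilevel modelling as predictors of final-session CAPS-5, within and between groups. No squared term, spline, categories or other functional form is stated. An exploratory sentence in the same section mentions developing individualised algorithms for optimal engagement, without a method.

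**The coach procedure.** In section 10.0 a patient is "optimally engaged in the exercise, as demonstrated by increasing physiological (e.g. skin conductance, heart rate) and subjective (increase in SUDS scores) indices". In that case the coach gives "encouragement to continue but will not interrupt the patient". The listed reasons to intervene concern lack of engagement. Over-engagement has no explicit branch.

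**The concern.** If response is best at some middle level of engagement, the relation to outcome is curved. A straight-line slope then reflects mainly where the sample lies relative to the peak. With the sample centred on the peak, the slope is near zero and the trial could report that engagement does not matter. With most of the sample below the peak, the slope is positive and the trial could report that more is better, although its own rationale says that too much is harmful. The analysis as described would not separate the two accounts that the protocol gives, and a reader could carry the second conclusion into how the system is used.

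**Working it through.** **Inputs from the documents.** Two-sided alpha is 0.05 and 32 participants remain after 20% attrition of 40 (section 11.0). Final CAPS-5 is one value per participant, so about 32 people inform the between-person relation. The plan gives no effect size, sample size or power for Hypothesis 3, so there is no figure to reproduce. The one power statement concerns the treatment comparison.

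**Assumptions, not in the documents.** Engagement x is standard normal. The outcome is scored as improvement, with total variance 1. Baseline severity correlates 0.5 with outcome and so explains 0.25 of the variance. Engagement explains a share R² of 0.10 or 0.25. Residual variance is 1 − 0.25 − R², that is 0.65 or 0.50.

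**What a straight line can see.** Let improvement contain −b(x − c)², with the peak c SD above mean engagement. Expanding gives −bx² + 2bcx − bc². For standard normal x, Var(x²) = 2 and Cov(x, x²) = 0. The best-fitting slope is therefore 2bc, and the share of the curve's variance that a line captures is 4c²/(2 + 4c²):

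- c = 0: 0/2 = 0
- c = 0.5: 1/3 = 0.33
- c = 1: 4/6 = 0.67

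The low and high ends cancel completely only at c = 0.

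**Simulation, n = 32, baseline-adjusted, several thousand trials per cell.**

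| Optimum | R² | Linear slope significant | Squared term significant |
|---|---|---|---|
| At the mean | 0.10 | about 10% | about 46% |
| At the mean | 0.25 | about 17% | about 81% |
| 1 SD above | 0.10 | about 37% | about 21% |
| 1 SD above | 0.25 | about 76% | about 48% |

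With the optimum at the mean, the significant slopes split about evenly by sign. With it 1 SD above, they are essentially always positive. Repeat runs moved these figures by up to about 3 to 4 points.

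**Sensitivity.** Without the baseline covariate and with R² from 0.10 to 0.30, the slope is significant in 9% to 16% of trials (optimum at the mean) and 31% to 73% (1 SD above). The squared term is significant in 36% to 81% and 16% to 43% respectively. The pattern is the same.

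**Price of a joint test.** If the relation is truly linear, testing the linear and squared terms together on 2 df lowers power from 54% to 43% at R² = 0.10 (11 points) and from 95% to 90% at R² = 0.25 (5 points).

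**How often the check stays silent.** With the optimum 1 SD above the mean, the squared term is non-significant in 100 − 48 = 52% to 100 − 21 = 79% of trials.

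**The case against.** The directional hypothesis is not arbitrary. Section 2.0 cites evidence that greater activation goes with better outcome, and Hypothesis 3 follows from it. That stands: the protocol holds two premises, and the optimum is not its only one. It is also why the analysis should be able to tell them apart.

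A reader might infer that the plan prescribes a straight line. It does not. The form of the model is left open, and linearity is only implied by the directional wording and the absence of any curved term. The published methods cited for calculating the measures are not available here.

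The optimum has a place in the exploratory analyses. It does, but with no form or test attached. If the optimum differs between patients, a single pooled squared term would not estimate it, so the check is partial.

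The sample is small, and this objection carries weight. The squared term has limited power, especially with an off-centre peak. Coaching three quarters of participants towards optimal engagement could also narrow the range of engagement and lower power further.

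A reader might infer from section 10.0 that coaches are told more activation is always better. The text does not go that far. It allows for variability between patients, gives its triggers as examples, and elsewhere lets the coach use the data to modify assignments without stating a direction. What can be said is that no over-engagement branch is written down. That is a matter of procedure and adds no weight to the statistical point.

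**Conclusion.** The conflict is in the text, and the plan names nothing that would resolve it. An optimum could be missed, or misread as 'higher is better'. The second is the more serious risk: with the optimum 1 SD above the mean, a positive slope is declared in about 37% to 76% of trials.

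These sizes rest on assumed variance shares of 10% to 25%, normally distributed engagement, a baseline correlation of 0.5 and 32 evaluable participants. They illustrate the risk and are not estimates for this trial.

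Two stronger readings are not supported. The low and high ends do not cancel in general, only when the optimum lies near the sample mean. Nor do the documents require the joint test to replace the linear one: that is a trade-off, given its cost if the relation is linear. The primary guided versus record-only comparison (Hypothesis 2) is unaffected.

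**What to change.** 1. State the functional form for Hypothesis 3 and keep the linear test as the formal test.
2. Pre-specify a centred squared term for mean HR, mean GSR and mean SUDS as a secondary check.
3. Report each fitted curve with its 95% confidence band over the observed range. A confidence interval for the turning point would often be unbounded at this sample size, so the band is the safer summary.
4. Limit any 'higher is better' conclusion to the observed range, and draw none for a measure whose squared term indicates curvature.
5. State in advance that the check has low power (under the assumptions above, about 46% to 81% with the optimum at the mean and 21% to 48% with it 1 SD above), so a non-significant squared term does not establish a straight line.

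The cost is three extra low-power exploratory tests on correlated measures. No new data are needed, and the linear test keeps its power. Making the 2-df joint test the formal one is optional and would cost about 5 to 11 points of power if the relation is linear.

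Separately, the study team must reconcile the aim of avoiding over-engagement in section 1.0 and the matching statement in section 2.0 with the coach procedure in section 10.0. No clinical rule is proposed here.

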**Assessments.** The instruments to be used were selected because many are standardized, have good psychometric properties, are widely used, and have been used by our research group. The primary outcome measures are described in this section. Information regarding additional measures can be found in Table 1.

Primary clinical outcomes include: the CAPS-5 for clinician-rated and PCL-5 for self-reported PTSD symptoms. The CAPS-5 is a 30-item structured diagnostic interview and gold standard for assessing PTSD (Weathers, Blake, et al., 2013). Independent evaluators blind to treatment condition will conduct the CAPS-5 at baseline, end of treatment, and follow up. The PCL-5 is a 20-item self-report measure that assesses PTSD severity each week and has excellent psychometric characteristics (Weathers, Litz, et al., 2013). IVE assessments include: psychophysiological reactivity (HR and GSR), which will be measured passively and continuously during IVEs using the patient worn data acquisition system (Zeriscope Inc.). Consistent with imaginal exposures, Subjective Units of Distress (SUDS; 0=no anxiety to 100=extreme anxiety) will be collected at 5-minute intervals during IVEs. A tone will signal patients to enter their SUDS using the device. Self-report questionnaires employed in our pilot feasibility study and other studies will assess comfort, acceptability, willingness to use, utility, and client satisfaction (Attikisson & Greenfield, 2004; Rizzo et al., 2010).

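### Hypothesis 3 models final CAPS-5 but leaves baseline CAPS-5 to an undefined, outcome-dependent covariate screen

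*Combined protocol and SAP*

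**What the plan says.** All the relevant text is under General Statistical Analyses in section 11.0, unless stated otherwise.

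- **Hypothesis 3:** "Higher levels of physiological and subjective engagement will predict greater treatment response". Section 1.0 makes the same question a milestone: to "identify how each of these indicators predicts treatment response".
- **Its analysis:** mean HR, GSR and SUDS go into multilevel models, "used to analyze these variables as predictors of CAPS-5 at final session within and between treatment groups". No baseline term is named.
- **Hypothesis 2, same final score:** "independent generalized linear mixed effects models will be used to examine PCL-5 and CAPS-5 scores at final session by group". The next sentence fixes the adjustment: "Models will be adjusted, respectively, for baseline PCL-5 and CAPS-5". It comes before Hypothesis 3 and belongs to the models with group as predictor.
- **General covariate rule:** "Baseline characteristics that are associated with the primary outcome measures will be included as covariates in subsequent analyses". It names no test, threshold or outcome time point.
- **Primary outcomes (section 10.0, Assessments):** "Primary clinical outcomes include: the CAPS-5 for clinician-rated and PCL-5 for self-reported PTSD symptoms". The rule can therefore reach baseline CAPS-5.
- **Randomization:** the urn scheme is stratified by baseline CAPS-5 total score.

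The Data Management and Analysis paragraph in section 13.0 adds no covariate rule and refers back to the statistical section.

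**The concern.** Someone who starts severe can improve a great deal and still finish with a higher score than someone who started mild. A regression of final CAPS-5 on engagement answers the question about response only if it holds baseline CAPS-5 constant. The plan does this for the randomized comparison. It does not do it for the engagement analysis, which needs it more: HR, GSR and SUDS during exposures are observed, not assigned, and may well track initial severity. Stratified randomization balances baseline severity between arms, not across levels of engagement.

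Under the general rule, whether baseline enters depends on the outcome data and on a criterion nobody has written down. If engagement and baseline severity are correlated and the screen misses baseline, the engagement slope is biased. A positive correlation hides benefit and a negative one overstates it. Two analysts following the same text could report different slopes for a stated milestone.

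**Working it through.** **Inputs from the documents.** 40 enrolled (section 6.0); 20% attrition, so 40 × 0.80 = 32; 3:1 allocation, so about 24 and 8 completers; two-sided alpha 0.05. The only power statement concerns the group comparison, so there is no Hypothesis 3 figure to reproduce.

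**Assumptions.** The documents give no correlations and no screening threshold. All values below are illustrative and in standardized units.

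**Model.** One mean engagement value E per participant, with correlation a to baseline B. Final = r·B − k·E + error, scaled to variance 1. Then:

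- raw baseline-final correlation = r − k·a
- engagement slope with B omitted = −k + r·a, so the bias is r·a

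For r = 0.5, a = 0.4, k = 0.4: the raw correlation is 0.5 − 0.16 = 0.34, and the slope without baseline is −0.4 + 0.2 = −0.20, half the true effect.

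**Simulation.** 100,000 trials per setting at n = 32. Screened: B is included only if its raw correlation with the final score has two-sided p<0.05. Always: B is included in every trial. True effect −0.4 (k = 0.4):

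| r | a | raw corr. | B included | mean slope, screened | power, screened | power, always |
|---|---|---|---|---|---|---|
| 0.5 | 0.4 | 0.34 | 49% | −0.32 | 0.43 | 0.60 |
| 0.3 | 0.4 | 0.14 | 12% | −0.30 | 0.39 | 0.55 |
| 0.66 | 0.4 | 0.50 | 85% | −0.37 | 0.61 | 0.68 |
| 0.7 | 0.4 | 0.54 | 91% | −0.38 | 0.67 | 0.71 |
| 0.5 | 0.2 | 0.42 | 69% | −0.37 | 0.63 | 0.70 |
| 0.5 | 0 | 0.50 | 85% | −0.39 | 0.75 | 0.77 |
| 0.5 | −0.2 | 0.58 | 95% | −0.40 | 0.81 | 0.81 |
| 0.5 | −0.4 | 0.66 | 99% | −0.40 | 0.82 | 0.82 |
| 0.3 | −0.4 | 0.46 | 78% | −0.41 | 0.68 | 0.66 |

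**Variations.**

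- Looser screens in the first row: p<0.10 gives 0.48 and p<0.20 gives 0.53, against 0.60.
- Letting baseline pass on either CAPS-5 or PCL-5, first row: 0.44 to 0.45.
- All 40 analysed: 0.56 against 0.70 (first row), 0.75 against 0.78 (raw 0.50, a = 0.4), 0.85 against 0.86 (r = 0.5, a = 0).
- Group added to both models (24:8): each power drops 1 to 2 points, for example 0.41 against 0.58 in the first row.
- True effect −0.2, r = 0.5, a = 0.4: 0.15 against 0.20, inconclusive either way.
- Overstatement, true effect −0.2, r = 0.3, a = −0.4: mean slope −0.22, and −0.26 in the 41% of trials where baseline is missed.
- No true effect: the screened analysis rejects in 5 to 6% of trials.

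**Two readings of the text.** In the first-row setting, the models with and without baseline disagree on significance in 41% of simulated trials. An analyst who took the Hypothesis 3 sentence literally and never included baseline would, with no true effect, r = 0.5 and a = ±0.4, reject about 20% of the time. That figure does not apply to the screened analysis.

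**The case against.** - **Final score as outcome.** Modelling a final score to study change is standard when baseline is adjusted for, and Hypothesis 2 does exactly that. This stands. The defect is only that baseline is not fixed in the Hypothesis 3 model.
- **A route for baseline exists.** The covariate rule covers later analyses, baseline CAPS-5 is its most obvious candidate, and the plan sets alpha at 0.05 for all analyses, which could be read as the threshold. At a raw correlation of 0.5, baseline would enter about 85% of the time with 32 participants and 92% with 40. This limits the harm. But the alpha sentence is not tied to the screen, the test and time point would still be missing, and inclusion would still depend on the outcome data.
- **The large loss needs adverse inputs.** It takes a weak raw baseline-final correlation together with an engagement-baseline correlation near 0.4. True. In one setting with a negative correlation the screen even shows 2 points more power, though that partly reflects a biased slope.
- **The simulated model is simpler than the planned one.** The plan uses multilevel models and engagement measures computed by cited methods. The figures illustrate the mechanism and do not estimate this trial's loss.
- **Secondary status.** Section 1.0 lists predictors of change among the secondary objectives of a small preliminary trial. This lowers the stakes but does not close the gap.

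**Conclusion.** The concern holds. Baseline CAPS-5 is guaranteed in the Hypothesis 2 models but not in the Hypothesis 3 models of the same score, where the predictor is not randomized and confounding by initial severity is possible. Nothing elsewhere in the document closes the gap.

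The size is uncertain because the documents give neither the sign nor the size of the engagement-baseline correlation. Over the settings tried at n = 32 with a true effect of −0.4, the power difference runs from 17 points lost to 2 points gained through the screen. Bias matters most when more severe participants engage more strongly; overstatement in the opposite case is modest. Under a p<0.05 screen the problem is bias and, in some settings, lost power, not false positives. The change is worth making, but the point does not touch the primary group comparison.

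**What to change.** Add one sentence to the Hypothesis 3 analysis: every model of final CAPS-5 includes baseline CAPS-5 as a fixed covariate whatever the screen shows, with treatment group in the pooled model. This extends the plan's own Hypothesis 2 practice.

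No new data are needed, since Table 1 already schedules CAPS-5 at baseline. The cost is one residual degree of freedom per model. With 32 participants, intercept, engagement and group leave 32 − 3 = 29; adding baseline leaves 28. If a separate model is fitted in the record-only arm (about 8 completers), 8 − 2 = 6 becomes 5, which is tight but was already so. If baseline had no effect on the final score, always including it would cost about 1 point of power at a = 0 (0.64 to 0.63) and about 4 points at a = ±0.4 (0.59 to 0.55).
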